8.2. Efficacy Variables

Primary Efficacy Parameters:	
 i. The proportion of subjects with symptomatic laboratory-confirmed COVID-19 identified after start of treatment and before the end of the 6-week treatment period ii. The proportion of subjects with symptomatic laboratory-confirmed VRI identified after start of treatment and before the end of the 6-week treatment period
Secondary Efficacy Parameters:	
 i. Mortality due to COVID-19 or complications thereof ii. The proportion of subjects (with or without symptoms) testing positive for antibodies to SARS-CoV-2 at either of the Week 6 or Week 8 visits
Exploratory Efficacy Parameters:	Hospitalization due to VRI or complications thereof, mortality due to VRI or complications thereof, proportions of subjects experiencing acute respiratory illness (ARI), hospitalization due to ARI or complications thereof, mortality due to ARI or complications thereof.

8.3. Response Definitions

ARI:	≥ 0.5 increase from baseline in mean symptom score for the chest/respiratory FLU-PRO domain or ≥ 0.5 increase from baseline in mean symptom score for at least two of the following FLU-PRO [®] domains: body/systemic, nose, throat.
COVID-19:	ARI after start of treatment and before the end of the 6-week treatment period associated with detection of SARS-CoV-2 by RT-PCR assay of nasopharyngeal swab.
VRI:	ARI after start of treatment and before the end of the 6-week treatment period associated with detection of any respiratory virus by RT-PCR assay of nasopharyngeal swab.

8.4. Statistical Methodology

The statistical methodology is described briefly below and will be described in detail in the Statistical Analysis Plan.

8.4.1. Efficacy Analyses

Efficacy analyses will be based on a population consisting of all subjects randomized without a laboratory-detected viral respiratory infection at the baseline visit (intention-

to-treat or ITT population). All chi-square analyses will be calculated with appropriate continuity corrections.

There will be two primary efficacy analyses:

- The proportion of subjects experiencing COVID-19 in the NTZ treatment group will be compared to that of the placebo treatment group using a two-sided Cochran-Mantel-Haenszel (CMH) chi-square test ($\alpha = 0.049$).
- The proportion of subjects experiencing VRI in the NTZ treatment group will be compared to that of the placebo treatment group using a two-sided CMH chi-square test ($\alpha = 0.001$).

Secondary analyses will be performed as follows:

- The proportion of subjects experiencing COVID-19 or VRI for treatment vs control will be tested within strata using Pearson chi-square tests at an unadjusted $\alpha = 0.05$.
- Confidence intervals (95% confidence level) will be produced for the overall odds ratio and for the odds ratios for NTZ vs placebo for each stratum.
- Proportions of subjects experiencing mortality due to COVID-19 or complications thereof will be compared by treatment group using a two-sided Pearson chi-square test (unadjusted $\alpha = 0.05$).
- Proportions of subjects (with or without symptoms) testing positive for antibodies to SARS-CoV-2 at either of the Week 6 or Week 8 visits will be compared by treatment group using a two-sided Pearson chi-square test (unadjusted $\alpha = 0.05$).

Exploratory analyses will be performed as follows:

- Proportions of subjects experiencing each of the following will be compared by treatment group using a two-sided Pearson chi-square test (unadjusted $\alpha = 0.05$): (i) hospitalization due to VRI or complications thereof, (ii) mortality due to VRI or complications thereof, (iii) proportions of subjects experiencing acute respiratory illness (ARI), (vi) hospitalization due to ARI or complications thereof, (v) mortality due to ARI or complications thereof.

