4.2 Efficacy Analysis

4.2.1 Primary Efficacy Variables

This study has two primary endpoints: symptomatic COVID-19 disease and symptomatic VRI. The study-wise Type I error rate is 0.05, allocated $\alpha = 0.049$ to COVID-19 disease and $\alpha = 0.001$ to all VRI. In each case the hypotheses to be tested are

$$\begin{aligned}H_0: p_1 &= p_2 \\H_1: p_1 &\neq p_2,\end{aligned}$$

where p_1 represents the COVID-19 disease rate (or VRI rate) in the NTZ arm and p_2 represents the COVID-19 disease rate (or VRI rate) in the placebo arm.

Primary Analysis

The proportion of subjects experiencing symptomatic COVID-19 disease in the NTZ treatment group will be compared to the similar proportion in the placebo group using a two-sided CMH test with continuity correction at $\alpha=0.049$. The contingency tables will be provided with rates relative to the treatment margins. The common relative risk and the odds ratio between the treatment groups and 95% confidence intervals for these parameters will be provided. The analysis will be repeated by sex of subject (female or male), age group of subjects (18- 34 years, 35- 64 years, 65 years and older), and race of subject (white or non-white).

The proportion of subjects experiencing symptomatic VRI infections in the NTZ treatment group will be compared to the similar proportion in the placebo group using a two-sided CMH Chi-square test with continuity correction at $\alpha=0.001$. The contingency tables will be provided with rates relative to the treatment margins. The common relative risk and the odds ratio between the treatment groups and 95% confidence intervals for these parameters will be provided. The analysis will be repeated by sex of subject (female or male), age group of subjects (18- 34 years, 35- 64 years, 65 years and older), and race of subject (white or non-white).

While every effort will be made to compile the data in accordance with intent-to-treat, it is likely that some subjects will have missing endpoints. Subjects with missing outcomes data will be included in the primary analysis. The primary analysis will impute missing data as uninfected in each treatment arm. Best-case and worst-case sensitivity analyses will be performed as outlined in Section 2.3 above. In addition, a tipping point analysis will

be performed, imputing various levels of COVID-19 and VRI infection rates to missing values in the NTZ arm to determine the infection rate at which the study conclusions change.

Secondary Analysis

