4.2.2 Secondary Efficacy Variables

Statistical tests for the secondary efficacy variables will be performed only if the primary analyses of primary efficacy variables both reject the null hypothesis. These tests act as gatekeepers to the secondary efficacy tests. No allocation of study-wise α to the secondary tests is necessary.

The mortality rates due to COVID-19 or complications will be compared by stratum with a Pearson Chi-square test. The overall mortality rate due to COVID-19 or complications in the two treatment groups will each be compared using a CMH Chi-square test with continuity correction at $\alpha=0.05$. A 95% confidence interval for the pooled odds-ratio will be provided.

The proportion of subjects testing positive for SARS-CoV-2 antibodies at either Week 6 or Week 8 will be compared using Pearson Chi-square tests with continuity correction in each stratum. The contingency tables will be provided with rates relative to the treatment margins. The overall positive rates in the treatments will be analyzed with a CMH Chi-square test.

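### The protocol tests COVID-19 mortality and antibodies unconditionally at 0.05, the SAP tests them only if both primaries reject, and neither document says which rule governs

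*Protocol*

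**What the plan says.** **Protocol 8.4.1 (Efficacy Analyses).** Two secondary bullets cover these endpoints.
- Proportions with "mortality due to COVID-19 or complications thereof will be compared by treatment group using a two-sided Pearson chi-square test (unadjusted" alpha of 0.05).
- The antibody bullet has the same form: positivity "at either of the Week 6 or Week 8 visits will be compared by treatment group using a two-sided Pearson chi-square test (unadjusted" alpha of 0.05).

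Neither bullet depends on the primary results. The section opens with a general rule: "All chi-square analyses will be calculated with appropriate continuity corrections". Section 8.4 says the methods are given briefly and that the SAP will hold the detail.

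**SAP 4.2.1.** "The study-wise Type I error rate is 0.05", split as 0.049 for COVID-19 and 0.001 for VRI.

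**SAP 4.2.2.** "Statistical tests for the secondary efficacy variables will be performed only if the primary analyses of primary efficacy variables both reject the null hypothesis". It calls the primaries gatekeepers and adds: "No allocation of study-wise α to the secondary tests is necessary". The overall mortality comparison is a continuity-corrected CMH test at 0.05. For antibodies, "The overall positive rates in the treatments will be analyzed with a CMH Chi-square test", with no alpha and no mention of a correction in that sentence. Pearson tests are kept within strata for both endpoints.

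Neither document has a precedence clause.

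**The concern.** The two documents give opposite instructions whenever either primary misses: one orders a test at 0.05 and the other withholds it. The gate needs VRI to reject at 0.001, so the secondaries are also withheld when COVID-19 succeeds and VRI narrowly fails.

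Antibody positivity is the endpoint at stake. It counts infections with or without symptoms, so it could show a difference when the symptomatic endpoints do not. Unless the rule is settled in advance, a reader cannot tell whether a favourable antibody p-value is a planned secondary result or one that the plan had ruled out.

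The gate also leaves a question inside the SAP. Once it opens, two secondaries are tested with no order and no split of alpha.

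**Working it through.** **1. The plan's own figure.** 0.049 + 0.001 = 0.05. The study-wise rate in SAP 4.2.1 reproduces exactly and is fully spent on the primaries.

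**2. Inputs for the gate.** From SAP 1.3 and Protocol 8.1: COVID-19 1% and VRI 2% over six weeks, 80% reduction (relative risk, RR, 0.2), N=2,842 or about 4,000, and equal strata. I read 1% and 2% as placebo rates. That reading fits the event counts. The pooled COVID-19 rate is (1% + 0.2%)/2 = 0.6%, so 2,842 × 0.006 = 17 events and 4,000 × 0.006 = 24 events, against 17 and 23 in the documents. As a further check, the normal-approximation power for 1% against 0.2% with 1,421 per arm at 0.049 is 78.6%, against the stated 80.6%.

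**3. Probability that the gate is shut.** Simulation of 40,000 to 100,000 trials per scenario, with seven equal strata, continuity-corrected CMH, and VRI counted as COVID-19 plus other viruses. Gate open = COVID-19 p < 0.049 and VRI p < 0.001.

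| True RR (both primaries) | N=2,842 | N=4,000 |
|---|---|---|
| 0.2 | 38% | 14% |
| 0.4 | about 83% | about 64% |
| 0.5 | about 92% | about 84% |
| 1 (no effect) | over 99.9% | over 99.9% |

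By step 2, the 38% belongs to about 17 COVID-19 events and the 14% to about 24, the count at which the trial stops. A VRI placebo rate of 2.8% lowers the 14% to about 10%.

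The 0.001 level matters here. The documents give VRI power of 98.2%. With 2% against 0.4% and 1,421 per arm, power is 97.5% at 0.05 but 73.5% at 0.001, so the gate is harder to pass than the stated figure suggests.

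**4. What the conflict does to one result (assumed counts).** Antibodies positive in 40/2,000 on NTZ and 62/2,000 on placebo:
- |40 × 1,938 − 62 × 1,960| = 44,000
- less N/2 = 2,000, this leaves 42,000
- chi-square = 4,000 × 42,000² / (2,000 × 2,000 × 102 × 3,898) = 4.44, p = 0.035

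This is significant at 0.05 under the protocol. If VRI misses 0.001, it is not tested under the SAP.

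**5. Pearson or CMH.** On the same totals, corrected CMH gives p = 0.032 to 0.035, depending on how the cases fall across strata. In 40,000 simulated trials per scenario with assumed antibody rates, the two corrected tests disagreed at 0.05 in under 1% of trials. The gate drives the consequence; the choice of test hardly does.

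**6. Error once the gate is open.** Two tests at 0.05 each, both nulls true, taken as independent: 1 − 0.95² = 9.75%. This takes 0.05 for antibodies, which the SAP does not state.

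The figure is an upper one. With equal arms and all d deaths on placebo, the corrected chi-square is about (d − 1)²/d. That is 3.2 for d = 5 and 4.17 for d = 6, against a critical value of 3.84. Mortality therefore needs at least six deaths, all in one arm, in a trial that stops at 24 COVID-19 illnesses. If mortality cannot reject, the error is close to 5%.

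**The case against.** The strongest reply is that the SAP is meant to govern. Protocol 8.4 leaves detail to it, and the SAP (26 April 2024) is later and more specific than the last protocol amendment (26 October 2020). The protocol also uses the label unadjusted for its within-stratum and exploratory tests, so the natural meaning is a nominal p-value and not a confirmatory claim. Much of this stands. It limits the harm to how a secondary result is labelled and reported. It does not remove the conflict, because a gate withdraws a test that the protocol orders, and no sentence says that the SAP prevails.

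Four stronger readings are tempting, and the documents do not support them.
- *The protocol inflates the study-wise error to 0.15 (14.3% if independent).* The protocol states no study-wise rate. That sum charges nominally labelled tests to a budget set only in the SAP.
- *The SAP revision history omits the gate, so the gate is an undeclared departure.* That log records changes between SAP versions. A gate present from version 1.0 would not appear in it.
- *The antibody CMH is uncorrected.* The SAP sentence is silent, and the protocol's general rule asks for continuity corrections throughout.
- *Pearson against CMH changes the conclusion.* Step 5 shows that it almost never does.

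**Conclusion.** The plan is wrong as written on one decision rule: whether mortality and antibodies are tested when a primary misses. If the drug works as assumed, the documents disagree in about 14% of trials at N=4,000 and 38% at N=2,842. They disagree in most trials at RR 0.4 to 0.5 and in nearly all with no effect. These figures rest on 1% and 2% as placebo rates, equal strata, the same RR for both primaries and a fixed N. The antibody counts are illustrative, because the documents give no seropositivity rate.

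A second, smaller fault is that the SAP's statement that no alpha allocation is needed does not hold as written. The gate protects against false secondary claims when a primary null is true. It does not protect across two unordered secondaries when both primaries have truly rejected.

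The point concerns secondary endpoints and is cheap to correct. It does not touch the primary tests.

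**What to change.** Before unblinding:

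1. In SAP 4.2.2, state that it supersedes the mortality and antibody bullets of Protocol 8.4.1. Align those bullets at any next protocol amendment.
2. Use one rule for both endpoints: an overall two-sided CMH test stratified by the randomisation strata, with continuity correction, for inference only if the gate is open. If it is shut, report estimates and confidence intervals descriptively.
3. Give the antibody CMH sentence an explicit alpha and correction.
4. Test the two secondaries in a stated fixed order at 0.05, or by Holm, and replace the sentence on alpha allocation. If a fixed order is used, note that placing mortality first would probably block antibodies (step 6). Holm would require the smaller p-value to reach 0.025.

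**Cost.** Wording only for the SAP, with no change to data or sample size. A protocol amendment that is not purely administrative needs IRB approval under Protocol 16.3, so the SAP sentence can come first. Secondaries cannot be claimed when the gate is shut, which the SAP already accepts, and whichever secondary is tested second loses a little power. The documents do not show whether unblinding has taken place. If it has, the reconciliation should be dated and reported as made afterwards.

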8.4.2. Population Pharmacokinetics Analysis

On Week 3 and 6, the plasma samples will be collected before the morning dose (at the trough). These data will allow for analysis of relationships between trough plasma concentrations and clinical and virologic response.

Trough plasma concentrations of tizoxanide and tizoxanide glucuronide will be summarized descriptively for each of the treatment groups. Exploratory analyses will be conducted to evaluate the relationships between plasma concentrations and age, race, gender, body weight, body mass index, VRI and adverse events.

8.4.3. Safety Analyses

All randomized subjects who receive the study medication will be evaluated for drug safety. Safety analyses will be done descriptively.

9. INVESTIGATIONAL PRODUCTS

9.1. Drug Regimens, Administration and Duration

Group 1 (NTZ): Subjects will receive two NTZ 300 mg tablets b.i.d. with food (< 1 hour after food intake) and a B complex vitamin ([REDACTED]) b.i.d. for 6 weeks.

Group 2 (Placebo): Subjects will receive two placebo tablets b.i.d. with food (< 1 hour after food intake) and a B complex vitamin ([REDACTED]) b.i.d. for 6 weeks.

The food prior to drug intake should preferably be a high-fat meal, but at minimum a cereal bar.

All subjects will receive a vitamin B complex supplement one tablet twice a day (manufacturer's labeled dosing) to help mask any potential chromaturia attributed to NTZ and aid in maintaining study blinding.

9.2. Identity of Investigational Products

The active formulation for this study is a yellow, film-coated tablet that contains 300 mg NTZ plus standard excipients. The placebo tablet will have the same appearance and inactive ingredients as the active tablet.

The vitamin B complex supplement is [REDACTED] manufactured by [REDACTED]. The supplement will supply each subject with the following Percent Daily Values based on a 2,000-calorie diet: vitamin B1 1,333%, vitamin B2 824%, vitamin B3 240%, vitamin B5 360%, vitamin B6 1000%, vitamin B7 100%, vitamin B12 15,000%, folate 100%, and vitamin C 267%.

9.3. Packaging and Labeling

NTZ or placebo tablets will be packaged in white 30 cc HDPE bottles, each containing 20 tablets. Each subject will receive a boxed kit containing 180 tablets (9 bottles). The subjects will take two tablets with food at each dosing time point. The kits will be stored at room temperature and will bear labels with the following information:

Table 6: Study Medication Labels

External Box Label

		Principal Investigator:
9 Bottles (20 Tablets Each)		
180 Tablets Total	Study N° RM08-3007	Treatment N°: XXXX
Lot:		

Take 2 Tablets by Mouth with Food Twice Daily Caution: New Drug-Limited by Federal Law to Investigational Use STORE AT ROOM TEMPERATURE • DO NOT USE BEYOND END OF STUDY KEEP OUT OF REACH OF CHILDREN Study Sponsor: The Romark Institute for Medical Research
		

Individual Bottle Label

20 Tablets	Study N° RM08-3007	Treatment N°: XXXX
Lot:		

Take 2 Tablets by Mouth with Food Twice Daily Caution: New Drug-Limited by Federal Law to Investigational Use STORE AT ROOM TEMPERATURE • DO NOT USE BEYOND END OF STUDY KEEP OUT OF REACH OF CHILDREN Study Sponsor: The Romark Institute for Medical Research
		

9.4. Drug Accountability

Medication will be dispensed at baseline. Medication compliance will be reviewed with each subject at each scheduled and unscheduled visit, subjects will be asked to return the bottles in which the medication was dispensed along with any unused medication.

The Investigator or designee is required to maintain adequate records of the disposition of all study drug, including dates, quantity and use by subject. Unused supplies must be returned to the Sponsor.

9.5. Subject Compliance

Subject compliance with the protocol will be checked by the Investigator and recorded in the EDC system at each visit.

Subjects will be considered non-compliant if they have missed more than 20% of the doses of the study medication (major protocol violation). Non-compliance will not be cause for discontinuation of subject participation in the study.

9.6. Disallowed Medication

During the active treatment course of the study, concomitant use of medications considered major CYP2C8 substrates are prohibited, see below.

Table 7: Major CYP2C8 Substrates

Generic Name	Brand Name(s)	Therapeutic Use and/or Drug Class
Amodiaquine	BASOQUIN, CAMOQUIN, FLAVOQUIN	Antimalarial
Daprodustat (GSK1278863)	*	Antianemic, prolyl hydroxylase inhibitor
Dasabuvir (ABT-333)	EXVIERA	Antiviral, NS5B inhibitor
Enzalutamide	XTANDI	Anticancer, antiandrogen
Montelukast	SINGULAIR	Antiasthmatic, LTRA
Pioglitazone	ACTOS	Antidiabetic, PPAR- γ agonist
Repaglinide	NOVONORM, PRANDIN	Antidiabetic, meglitinide analog
Source: Backman et al. 2016 .		
*Currently listed as investigational only and not yet granted a trade name by the manufacturer.		

Subjects are also prohibited from taking hydroxychloroquine, chloroquine, NTZ (except as the blinded investigational medication) or any other investigational medication or vaccine during the study. Since tizoxanide is highly protein-bound and may compete with plasma protein binding sites, co-administration of NTZ and warfarin should be avoided if reasonably possible. If co-administration of NTZ and warfarin cannot be avoided, the investigator must monitor prothrombin time and international normalized ratio (PT/INR) in subjects taking warfarin as clinically warranted.

Medications for pre-existing conditions that are not excluded (see exclusion criteria) should be continued as prescribed. The use of such medication will be recorded in the EDC system.

10. ADVERSE EVENTS

The term “adverse event” is defined for purposes of this study as any unwanted physical, psychological or behavioral change experienced by a subject during the course of the study and after taking the first dose of study medication regardless of its severity or relation to the study. Adverse events may include symptoms, signs, unexpected worsening of pre-existing conditions, clinically significant changes in laboratory values, diseases and syndromes, and significant and unexpected failures of pharmacological action of other medications. Symptoms of VRIs (cough, sore throat, nasal obstruction, fatigue, headache, myalgia, feverishness) and complications of VRIs will not be reported as adverse events.

Adverse events will be recorded on the appropriate EDC forms throughout the study, and the severity of each adverse event will be graded on a four-point scale: mild, moderate, severe, or life-threatening (See [Appendix II](#)). The duration of the adverse event and relationship to the study drug will also be recorded. All adverse events must be followed until their resolution or stabilization even beyond the planned study period.

